8.8 Monitoring Plan

The monitoring schedule and documents viewed are detailed in a separate document *“Monitoring Plan”*.

9 Statistical Considerations

For primary, secondary and tertiary study objectives an Intra subject endpoint comparison is used: All pairwise comparisons are of interest i.e. preimplant to 12 months postimplant, preimplant to 18 months postimplant, and the change from 12 to 18 months.

The power analysis applied for the study design was based on an available data set (n= 67, Cochlear-IROS data) of repeated measures on the HUI3, collected for elderly CI-patients, at preimplant and 12 months post implant intervals. The HUI 3 will serve as the primary outcome measure for this study to measure the added health utility gain for the multi- attribute health status from preimplant (@ \leq 2 months first activation) to the postimplant (@ 12 months post activation) interval in a population of implanted 60+ year olds.

The minimum clinically important change over two intervals for the HUI3 is 0.03 units on a scale of 0 representing poor health and 1.0 representing full health.

The power calculations were performed using the free package G*Power 3.1 by a consultant statistician at the Macquarie Sydney University.

The differences observed for the implanted elderly population in the existing Cochlear IROS dataset demonstrated a mean change = 0.165 at 95% confidence interval, with a range of 0.109 to 0.221 and a non-normal distribution for the cohort of 67 implanted elderly recipients over the age of 60 years examined.

Using this information to estimate the sample size required for significant changes on the HUI3 multi attribute score, *for intra subject comparisons of endpoints*, aiming for a change of \geq 0.10 units between the two test intervals, and a power of 90% and using a two-side paired t-test to calculate the 5% significance level, a sample of N=68 is required for the multi-attribute health utility. For comparison of changes in self ratings individual health domains of the HUI3, aiming for a power of 80% a sample of N=100 is required.

Study statistical analysis plan is available as separate document.

10 Data Management

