The aim, as described in the protocol, is to provide transparent and comparable medical evidence that can support health care policy makers to take informed decisions on the provision of health services for the treatment of hearing loss. A brief summary of the protocol follows.

3. Objectives of the Study

The primary objective is to evaluate the change in health-related quality of life following CI treatment by using the generic Health Utilities Index Mark III (HUI 3) multi-attribute index score. All pairwise comparisons are of interest i.e. preimplant to 12 months postimplant, preimplant to 18 months postimplant, and the change from 12 to 18 months.

A secondary objective involves evaluating the impact of CI treatment in the elderly on domains that may be associated with healthy aging and overall well-being such as

- hearing ability (using the Capabilities of Auditory Performance (CAP-II) test, the Speech Spatial and Qualities (SSQ) questionnaire, the Hearing Handicap Inventory for the Elderly Scale (HHIE-S), speech recognition tests in the quiet and in noise, pure tone audiometry (PTA) and sound field thresholds (SFT))
- independence (using the Lawton-instrumental Activities of Daily Living (L-iADL) tool)
- cognition (using the Mini Mental State Examination (MMSE) score, the Digit Symbol Substitution (DSST) test and the Trail Making Test version B (Trail B))
- falls (using the Timed Up and Go test (TUG))
- depression (using the Geriatric Depression Scale-15 (GDS-15), and the De Jong Loneliness Scale)
- CI usage measures.

All pairwise comparisons between time points, as defined above, are of interest here also.

A tertiary objective is to identify healthcare resource utilisation that is impacted by comparing costs post CI treatment with those prior to treatment.

For all of these objectives, interest is also in whether various demographic variables are associated with the change in outcome scores observed.

In summary:

Primary hypothesis

CI treatment significantly improves the overall health related quality of life of elderly individuals compared to their pre-implant condition (and again from 12 to 18 months following surgery) as measured by the HUI3 multi-attribute score.

Secondary hypothesis

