CI treatment significantly impacts healthy aging domains and wellbeing of elderly individuals compared to their pre-implant condition (and again from 12 to 18 months following surgery) as measured by clinically standard evaluation tools in the geriatric and audiological fields (as described above)

Tertiary hypothesis

CI treatment significantly reduces healthcare resource utilisation in elderly individuals over time.

Other hypotheses

There are covariates associated with the change in health-related quality of life and other healthy aging domains and related well-being.

4. Study Design

The study is a prospective observational longitudinal study performed to evaluate the benefits for overall health following CI treatment in the elderly population treated in routine clinical practice. Multiple centres are included in the study

Implantation with commercially available cochlear implant devices (i.e. products approved for market release) available for routine clinical treatment of deafness in all ages in collaborating investigator clinic sites is made as part of the study and no additional interventions are applied.

Change in outcome scores for various standard assessment tools and health domains post CI treatment compared to the pre-implant status are made using participants as their own controls. All questionnaires of interest are administered at each visit (up to 2 months pre-implant, 12 months post-implant [+/- 1 month] and 18 months post-implant [+/- 1 month]).

Whilst a recommended evaluation schedule is provided, participating clinics may select the optional evaluation measures they wish to use for their patients from the tools made available on the study specific electronic platform at baseline registration of each patient.

Participating in the study is voluntary and the participant is free to electively cease participation in the registry at any time. To be included in the study, participants must meet all local and study specific inclusion criteria and have none of the exclusion criteria. Participants remain in the study for a period of up to 2 years.

5. Sample size

Assuming that a paired t-test of the change in HUI3 multi attribute score from pre-implant to 12 or pre-implant to 18 months following implantation is of interest, then with 90% power and a 5% level of significance a change of 0.1 with standard deviation of change equal to 0.25, would require 68 participants.

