7.2 Summary Statistics

In preliminary work, summary statistics and plots should be examined for each variable to be included in a given analysis at each time point. This helps to describe the population and identify potential issues with the data. Appropriate summaries include:

- For one categorical variable (such as CAPII, gender, work status, education level) the count and proportion of participants in each category of the given variable should be tallied and the mode could be identified. Bar charts should also be created.
- For one continuous or discrete (integer only) variable (for example HUI3 multi attribute score, out of pocket costs, smoking level, age) the mean, standard deviation, median and interquartile range (IQR) could be calculated. Boxplots and histograms can be used to summarise the continuous and discrete (including response) variables.
- Non-normality of a given response at any time point is not necessarily a problem since the analysis to be used does not make assumptions about the distribution of the response scores.

For the primary and secondary hypotheses

- The change in the response variable over time should be examined by using boxplots with the response as the y-axis and time as the grouping variable or using scatterplots with a longitudinal trend included. Each persons' observations could be joined to show the variability in individual response over time. The purpose of this is to determine whether a linear change over time is apparent. This will impact on the form of the analyses undertaken.

For the tertiary and other hypotheses

- For categorical predictors of interest, boxplots at each time point should be used to determine whether the response variable (on the y-axis) appears to indicate differences between the categories (on the x-axis) of the categorical predictor.
- For continuous predictors of interest, scatter plots at each time point should be used to determine whether a relationship between the response variable (on the y-axis) and the predictor variable (x-axis) is evident.

The purpose of the above steps is to investigate the relationship between the predictor variable and the given response variable.

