7.3 Statistical Analyses

Primary hypothesis analysis

If comparison between the HUI3 multi-attribute score from pre-surgery to only one follow-up time point is of interest then paired t-tests can be used. A check of the assumption that the change from pre-surgery is normally distributed should be performed. The distribution of change scores should be approximately symmetric. The disadvantage of this approach is that it uses only complete data at any given pair of time points

If all pairwise differences are of interest (as per the hypothesis) and the scatter plot of change over time appears (close to) linear then a linear mixed-effects model with a fixed effect of time (treated as a continuous variable) and a random effect for participant should be used to explain the change in response variable over time. Tukey pairwise differences between time points can be specified (we recommend using the *multcomp* package in R as it does not require balanced designs i.e. the same sample size across time points). Appropriate diagnostic checks of the linear mixed-effects model (for example, normality of the residuals, normality of the random effects) should always be undertaken. An advantage of the linear mixed-effects model is that it uses all available data even for subjects who have dropped out at a given time point and then returned.

If the change over time was evidently not linear from the scatterplot of response against time then alternative approaches should be used. For example:

1. A quadratic or cubic term for time could be added to the linear mixed-effects model and checked to determine if that improves the fit of the model (eg via reduced AIC, better diagnostic checks).
2. The pre-surgery HUI3 multi attribute score value can be used as a predictor variable (with the response variable then only including the post-surgery visits). A significant coefficient would imply that the amount of change is dependent on the pre-surgery score. An interaction between baseline score and post-surgery time points could also be included – this would show whether the change in mean score over time is impacted by baseline score. This approach will remove any participant without baseline data from the analysis.

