3. Use visit as categorical variable. This essentially fits a linear model between time points but makes no assumption that the change from baseline is linear. Tukey pairwise comparisons between all pairs of time points (if time is found to be a significant predictor) are straight forward with this approach and should be undertaken using the *multcomp* package in R, which does not require balanced designs.

Secondary hypotheses analysis

The approach described for the primary hypothesis can be used for all continuous responses described in the secondary hypotheses. Failure of the assumptions may indicate that that a linear model is not appropriate and that other response distributions need to be explored. At this stage it is likely best that a statistician is consulted.

For ordinal responses such as the CAP II score an ordinal mixed-effects model including time as a fixed effect and participant as a random effect. The results of this model will show the

odds of being in a higher category compared to the current category over time (this interpretation is package dependent).

Tertiary hypotheses analysis

The approach described for the primary hypothesis is appropriate here also for continuous outcomes. As described above, for ordinal responses an ordinal mixed-effects model including time as a fixed effect and participant as a random effect. If the response variable is nominal (categorical without natural ordering) a multinomial mixed-effects model can be used and for binary responses a mixed effects logistic regression can be undertaken.

If only one pair of time points is of interest then for binary responses a test for the change in proportions can be undertaken and for continuous responses a paired t-test can be undertaken.

Analysis for other hypotheses

The other hypotheses involve the effect of covariates on a response and on the change over time. To assess the effect of a given covariate (for example age, gender, etc) the covariate can be added to the model as a fixed main effect in addition to the time variable and as an interaction with the time variable.

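### In the SAP's linear-time branch the three primary HUI3 comparisons are one slope test, so the 12-to-18-month change is not tested separately

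*SAP*

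**What the plan says.** Protocol 8.4 lists three comparisons under the primary end-point, including the second postimplant visit against the first. Protocol section 9 names them: "preimplant to 12 months postimplant, preimplant to 18 months postimplant, and the change from 12 to 18 months". SAP section 3 repeats this, and its primary hypothesis claims improvement over the preimplant state "and again from 12 to 18 months following surgery) as measured by the HUI3 multi-attribute score". SAP section 5 adjusts the significance level for three comparisons.

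SAP 7.3 (Primary hypothesis analysis) sets the model by a condition. Where every pair of visits is to be compared, which the SAP takes from its hypothesis, the model depends on whether "the scatter plot of change over time appears (close to) linear". For data that pass this reading of the plot, the instruction is: "a linear mixed-effects model with a fixed effect of time (treated as a continuous variable) and a random effect for participant should be used". It adds that "Tukey pairwise differences between time points can be specified".

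The plot is described in SAP 7.2: "The purpose of this is to determine whether a linear change over time is apparent". No numerical criterion is given. If the change is evidently not linear, SAP 7.3 offers three examples: a quadratic or cubic time term, baseline score as a predictor of the postimplant scores, and visit as a categorical variable. Of the last it says: "This essentially fits a linear model between time points but makes no assumption that the change from baseline is linear".

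**The concern.** A straight line through three visits cannot tell an early gain followed by a plateau from a steady gain. Once the continuous-time model is chosen, the 12-to-18-month result follows arithmetically from the overall slope, whatever happened between those two visits. A Tukey adjustment does not help, because there is only one distinct test to adjust.

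Two results are at stake. One is the claim of further improvement from 12 to 18 months, which would be carried by the pre-to-post effect. The other is the size of the gain at 12 months, which the line pulls down if the true course is a plateau. SAP 7.3 also extends the approach to the continuous secondary outcomes. The direction of the pre-to-post conclusion is not in doubt.

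**Working it through.** **Inputs from the documents**
- Visits at 0 (preimplant), 12 and 18 months.
- SAP section 5: "a change of 0.1 with standard deviation of change equal to 0.25", 90% power.
- Planned N = 100 and attrition of 5 to 10% (Protocol 8.6.7); 100 less 10% gives N = 90.
- Mean change of 0.165 in the earlier data set (Protocol section 9).
- Important change 0.03 and HUI3 range −0.36 to 1.00 (Protocol 5.2.1).

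**Assumptions not in the documents**
- The full gain *d* is reached by month 12 and nothing changes after.
- The SD of the 12-to-18 change, *s*, is 0.12, 0.20 or 0.25.
- SD of change is 0.25 from preimplant to either postimplant visit.

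**1. The plan's own figures.** An exact two-sided paired t-test gives 68 participants at 5% (power 90.2%) and 88 at 0.05/3 (power 90.3%), as the SAP states. These are sizes for separate tests.

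**2. The identity.** With mean *a + bt*, the contrasts are 12*b*, 18*b* and 6*b*, with standard errors 12, 18 and 6 times SE(*b*). Each has test statistic *b*/SE(*b*). The three are perfectly correlated, so a single-step adjustment leaves the p-value unchanged. A fitted example (simulated plateau, N = 100, 10 missing at month 18) gave contrasts of 0.070, 0.105 and 0.035, all with z = 4.092. With visit as a factor, the same data gave a 12-to-18 difference of −0.0001 (z = −0.002). Actual visit dates would change the multipliers but not the shared statistic.

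**3. What the line reports under a plateau.** Means (0, *d*, *d*); centred times −10, 2, 8; Sxx = 168; Sxy = 2*d* + 8*d* = 10*d*; *b* = 10*d*/168 = *d*/16.8.

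| True gain *d* | Pre to 12 (12*b*) | 12 to 18 (6*b*), true value 0 | Pre to 18 (18*b*) | Largest distance of a visit mean from the line |
|---|---|---|---|---|
| 0.10 | 0.071 | 0.036 | 0.107 | 0.021 |
| 0.165 | 0.118 | 0.059 | 0.177 | 0.035 |

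The pre-to-12 gain is understated by 1 − 12/16.8 = 29%. Both false 12-to-18 gains exceed 0.03.

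**4. How visible the plateau is.** The distances 0.021 and 0.035 are 0.09 and 0.14 of the SD of change (0.25), and 1.6% and 2.6% of the HUI3 range (1.36 units).

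**5. How often a false gain is declared.** The contrast free of intercept and slope is Y0 − 3·Y12 + 2·Y18, with mean −*d* and SD √(0.25² + 6*s*²). For *d* = 0.10 and *s* = 0.12 the SD is 0.386, its SE at N = 90 is 0.041, and the ratio is 2.46. A 5% test then misses the plateau about 31% of the time. A false gain means that the slope is significantly positive and lack of fit is not significant. With 20,000 simulated trials per setting, N = 90 and complete data, for *s* = 0.12 / 0.20 / 0.25:

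| Rule for entering the linear branch | *d* = 0.10 | *d* = 0.165 |
|---|---|---|
| 5% test of the contrast above | 31 / 59 / 69% | 2 / 19 / 35% |
| 5% test of a quadratic term in the random-intercept model | 66 / 68 / 69% | 13 / 26 / 35% |

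With no check the rate is 98–100% across these settings.

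**6. Visit as a factor.** With unstructured covariance and Tukey contrasts, a false 12-to-18 gain is declared in about 1% of trials, and power for a pre-to-12 gain of 0.10 is about 92% at N = 90.

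**7. Covariance under that model.** A random intercept alone forces one SE on all three differences, through the pooled SD √((2·0.25² + *s*²)/3). This is 0.216 for *s* = 0.12 and 0.235 for *s* = 0.20. Against 0.25, the pre-to-post SE is about 14% and 6% too small; against *s*, the 12-to-18 SE is about 80% and 17% too large.

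**The case against.** The defect arises in one branch only. If the plot is judged evidently not linear, all three alternatives free the 12-to-18 comparison: a quadratic is saturated in the mean at three nominal visits, and the baseline-as-predictor model has a time effect that is the 12-to-18 change. The SAP also asks for summaries at each visit and for model diagnostics. Under a plateau the 12- and 18-month summaries would look alike, so an analyst might well notice.

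The error rates depend on the rule assumed for reading the plot. Choosing by AIC, which the SAP mentions only for judging an added quadratic or cubic term, gives about 13–49% (*d* = 0.10) and 0.4–17% (*d* = 0.165). Calling the course non-linear when the observed 12-to-18 rate is under half the pre-to-12 rate gives about 5–21% and 0.4–8%. Finally, the synopsis endpoint, the protocol's primary hypothesis and the sample size effect all concern change from preimplant.

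Much of this is fair. The rate under visual reading is unknown, and the 98–100% figure describes no check at all. But neither stricter rule is the SAP's rule for entering the linear branch, and the diagnostics it names are normality checks. The single-test identity depends on no plateau or SD assumption. The synopsis does not remove a comparison that Protocol 8.4, Protocol section 9 and SAP section 3 all include.

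**Conclusion.** The concern holds and should be corrected. Within the linear branch, a comparison listed as primary is not tested separately; this is exact for any trajectory. Entry to that branch rests on an undefined reading of outcome data.

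The size depends on an assumed plateau after month 12 and an assumed 12-to-18 SD of 0.12–0.25, with N = 90 and an SD of change of 0.25. On those terms a false 12-to-18 gain above the 0.03 threshold is reported in 31–69% of trials (true gain 0.10) or 2–35% (0.165), even after a formal 5% lack-of-fit test. The documents give no 18-month data with which to narrow this. The claim of later improvement and the size of the 12-month gain are affected; the direction of the pre-to-post result is not.

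**What to change.** Make the SAP's third alternative the only pre-specified primary model: visit as a three-level factor, with the three visit contrasts tested by the single-step Tukey method in *multcomp* at a family-wise 5%. State that this replaces, for the primary endpoint, the other adjustment options in SAP section 5 and the Multiple Comparisons section. Delete the plot-based choice and the continuous-time and quadratic or cubic options from the primary analysis. Use the same visit coding for continuous secondary outcomes.

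As a separate addition, specify an unstructured within-participant covariance fitted by REML, so that each difference has its own standard error.

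The cost is SAP wording, plus 6 covariance parameters instead of 2. No extra participants are needed: the SAP already allows for three comparisons with 88 participants, and power on that Bonferroni basis is about 91% at N = 90.

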Because all pairwise tests are of interest one method for undertaking this is to perform multiple tests and then adjust the significance level for the number of comparisons (in this case 3). This is equivalent to having a significance level of $0.05/3 = 0.0167$ and is a form of Bonferroni correction. If we recompute the sample size required with this significance level then at least 88 participants would be needed to find a change of 0.1 units in the HUI3 significant.

6. Study outcomes

The outcomes measures described in section 3 are detailed in the Protocol document and are briefly described here. This section could be updated when a better understanding of the distribution of the outcome measures is obtained through the data collected.

HUI 3

The HUI3 is a 15-item questionnaire. Responses to items are converted to levels and a scoring function applied. The ultimate result is a series of domain scores and a multi-attribute score. Domain scores typically don't have continuous distributions and need to be analysed with care. The multi-attribute score may be treated as continuous and is the focus of this study. Higher scores indicate less impairment.

CAP-II

The CAP-II comprises 9 questions placing each participant into one of 10 ordinal categories that determines their auditory performance at the time of assessment. Scores range from 0 (no awareness of environmental sounds or voice) through to 9 (use of telephone with unknown speaker in unpredictable context) so that higher scores imply better performance. These scores are an ordinal categorical scale and should not be treated as continuous.

SSQ

The SSQ is a 49-item questionnaire utilising a 10-point numerical rating scale for each question. The SSQ comprises three main subscales; speech perception (using the first 14 questions), spatial hearing (using the next 17 questions) and other qualities of hearing (using the last 18 questions).

Each subscale is the average of the scores from each subscale item; so, for example, scores on the speech component are between 0 and 10. These scores may be assumed to be continuous, higher scores imply better performance.

HHIE-S

The HHIE-S is a 10-item short form that assesses the impact of hearing impairment on emotional and social adjustment. Higher scores indicate greater handicap. The distribution is described as continuous.

Speech recognition in quiet

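### For all pairwise HUI3 changes the SAP names only a participant random effect, which forces one variance on three change scores, and it plans no check of that

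*SAP*

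**What the plan says.** Three HUI3 comparisons are of interest. The SAP's primary hypothesis (section 3) covers improvement over the pre-implant state "and again from 12 to 18 months following surgery) as measured by the HUI3 multi-attribute score". Protocol section 9 likewise lists "preimplant to 18 months postimplant, and the change from 12 to 18 months", and Protocol 8.4 has the same three comparisons. The 12-to-18 month contrast is not in the synopsis primary endpoint or in the primary hypothesis of Protocol 7.1.

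For this all-pairwise case SAP 7.3 (Statistical Analyses) directs that, when change looks close to linear, "a linear mixed-effects model with a fixed effect of time (treated as a continuous variable) and a random effect for participant should be used". When it does not, three alternatives are offered. The first adds polynomial time terms. The second uses the baseline score as a predictor and is outside this point. The third reads "Use visit as categorical variable. This essentially fits a linear model between time points", with Tukey comparisons if time is a significant predictor. The first and third change how time enters the mean; neither mentions the within-subject covariance. Diagnostics are required, with two examples, both about normality: "for example, normality of the residuals, normality of the random effects) should always be undertaken".

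The sample-size section (SAP 5) treats the case where "the change in HUI3 multi attribute score from pre-implant to 12 or pre-implant to 18 months following implantation is of interest" and assumes "a change of 0.1 with standard deviation of change equal to 0.25". For the three comparisons it adds that "one method for undertaking this is to perform multiple tests and then adjust the significance level for the number of comparisons". Neither document gives an SD for the 12-to-18 month change.

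**The concern.** A participant random intercept with independent, equal-variance residuals implies the same variance for the difference between any two visits. Two of the three differences here span surgery and a year or more. The third compares two post-implant visits six months apart. Equal variances should not be taken for granted, the SAP does not say that it assumes them, and no figure in either document supports them.

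If the 12-to-18 change varies less than the other two, a common variance makes the pre-to-post intervals too narrow. With visit as a factor it also makes the 12-to-18 interval too wide, so a modest late gain is harder to detect. If it varies more, these errors run the other way. At stake are the accuracy of the reported HUI3 intervals and, under the categorical-visit alternative only, power for the 12-to-18 contrast.

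**Working it through.** **The plan's own figures.** A two-sided paired t-test for a change of 0.10 with SD 0.25 and 90% power (noncentral t) needs 68 subjects at alpha 0.05 (power 0.902) and 88 at 0.05/3 (power 0.903). Both SAP figures reproduce and are not in question. The earlier data set in Protocol section 9 (n = 67, 95% interval 0.109 to 0.221, half-width 0.056) implies an SD of 0.056 × √67 / 1.997 = 0.230, but only for pre-to-12 months.

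**Inputs.** Pre-to-post SD 0.25 (SAP 5). n = 90, that is 100 enrolled less the upper 10% attrition (Protocol 8.6.7). Visits at 0, 12 and 18 months. The 12-to-18 SD, *s*, is **assumed**: 0.30, 0.25, 0.19, 0.16 or 0.11.

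**Visit as a factor.** The random intercept gives Var(Yj − Yk) = 2σ² for every pair. With complete data its estimate is the average of the three change variances, so the common SD is √((2 × 0.25² + s²)/3). At s = 0.16 this is √(0.1506/3) = 0.224. The model SE is then 0.224/0.25 = 0.90 times the true one for pre-to-post and 0.224/0.16 = 1.40 times for 12-to-18. Coverage of a nominal 95% unadjusted interval is P(|Z| < 1.96 × ratio), about 92% and 99%. One REML fit to simulated data (n = 88) confirmed the mechanism: the contrasts' own SEs were 0.0266, 0.0274 and 0.0150, and the model gave 0.0237 to all three.

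**Continuous time.** Centred times are −10, 2 and 8, with sum of squares 168. When the mean is linear, the true slope variance per subject is (100 × 0.25² − 16s²)/168², and the model's is (2 × 0.25² + s²)/(6 × 168). At s = 0.16 these are 2.07 × 10⁻⁴ and 1.49 × 10⁻⁴, so the SE ratio is √(1.49/2.07) = 0.85 and coverage is P(|Z| < 1.96 × 0.85) = 90%. All three contrasts are multiples of this slope and share the ratio.

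**Power for a 12-to-18 gain of 0.05 (Tukey).** At s = 0.16 with visit as a factor, the estimate must exceed 2.363 × 0.224/√90 = 0.056, while its true SE is 0.16/√90 = 0.0169; power is about 37%. With its own variance the threshold is 2.384 × 0.0169 = 0.040 and power is 72%. In the continuous-time model a linear gain of 0.05 over six months is a slope of 0.0083 with true SE √(2.07 × 10⁻⁴/90) = 0.0015, a ratio of 5.5, so power is about 100%.

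| Assumed s | 0.30 | 0.25 | 0.19 | 0.16 | 0.11 |
|---|---|---|---|---|---|
| Factor: SE ratio, pre-to-post | 1.07 | 1.00 | 0.93 | 0.90 | 0.86 |
| Factor: SE ratio, 12-to-18 | 0.89 | 1.00 | 1.22 | 1.40 | 1.94 |
| Factor: coverage %, pre-to-post | 96 | 95 | 93 | 92 | 91 |
| Factor: coverage %, 12-to-18 | 92 | 95 | 98 | 99 | 100 |
| Factor: power %, 12-to-18 gain 0.05 | 30 | 32 | 35 | 37 | 40 |
| Own variance: same power % | 22 | 32 | 55 | 72 | 97 |
| Continuous time: SE ratio | 1.12 | 1.00 | 0.89 | 0.85 | 0.80 |
| Continuous time: coverage % | 97 | 95 | 92 | 90 | 88 |
| Continuous time: error % of nominal 5% slope test | 3 | 5 | 8 | 10 | 12 |

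The higher factor-model power at s = 0.30 comes from an SE that is too small.

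**Familywise error** (simulation, visit as a factor, Tukey, all changes null) runs from about 5% to 6.5% over this range. Requiring time to be significant first, as SAP 7.3 does, brings it to roughly 4.5 to 6%.

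**With attrition.** In 600 REML fits (n = 100, 5% missing at month 12 and 10% at month 18, at random, s = 0.16), coverage for pre-to-12, pre-to-18 and 12-to-18 was 92.0, 91.8 and 99.3% with the random intercept, and 95.5, 94.0 and 96.5% with an unstructured covariance. Simulation error is about 0.9 points, from √(0.95 × 0.05/600).

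**The case against.** The strongest reply is that this is a conditional weakness. The 12-to-18 SD is unknown, the error vanishes at 0.25, and it reverses above. That stands, and it is why a range is shown.

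A reader might infer that the model named first loses power for the 12-to-18 gain. It does not: if change is linear, power for a 0.05 gain is about 100% at every assumed SD. The power loss belongs to the categorical-visit alternative. In the continuous-time model the harm is to coverage and test error only.

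A reader might also infer that the SAP rules out a covariance check. It does not. The diagnostics list is open, and section 7.2 suggests SDs at each time point and joined individual profiles. The stated purpose of those profiles is to judge linearity, however, and no step leads from them to the covariance.

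Paired tests with a Bonferroni adjustment use each contrast's own variance and escape the point. The sample-size section offers them as one method, but SAP 7.3 directs all-pairwise analyses to the mixed model.

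Nor do the documents support the inference that false positives are seriously inflated. Familywise error rises little. With a true pre-to-post effect of 0.10 and no later change, the 12-to-18 Tukey error is 3.7/1.9/0.5/0.1/0.0% across the assumed SDs, never above 5%.

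Finally, naming the random effect does specify a model, so the equal-variance assumption is implicit and not hidden. That is fair, but an implicit assumption that is neither justified nor checked still merits a sentence.

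**Conclusion.** The point holds and is minor. The only within-subject term named for the all-pairwise HUI3 analysis imposes equal change-score variances that no document figure supports. For assumed 12-to-18 SDs of 0.11 to 0.30, coverage of nominal 95% intervals runs from 88 to 97% in the continuous-time model. With visit as a factor it runs from 91 to 96% for pre-to-post and from 92 to almost 100% for 12-to-18. The results rest on a pre-to-post SD of 0.25, 90 complete subjects, a linear mean in the continuous-time case, and reading the random effect as an intercept.

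The documents do not support concluding that the sample sizes are wrong or that the main pre-to-post finding is in doubt. The earlier mean change of 0.165 is large against these SE errors. SAP 7.3 lets the same approach be used for continuous secondary outcomes, but no change SDs are given for them, so the effect there cannot be sized.

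**What to change.** Whichever time term is used, replace the lone participant random intercept with an unstructured 3x3 within-subject covariance, fitted by REML with Kenward-Roger or Satterthwaite degrees of freedom, for HUI3 and the continuous secondary outcomes. Keep the multiplicity-adjusted pairwise contrasts. Report the three change-score SDs so that a reader can see whether they differ. The model still uses all available data, as SAP 7.1 requires.

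The cost is SAP wording and four extra variance parameters (six instead of two) with about 90 to 100 subjects. If the three SDs are equal, almost nothing is lost: with visit as a factor, power for a 12-to-18 change of 0.10 is 92% either way.

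Making visit categorical throughout is a separate, optional choice. It is safer for distinct pairwise contrasts, but it has a price if change really is linear: power for a 0.05 gain from 12 to 18 months falls from about 100% to 72% at an SD of 0.16 and to 32% at 0.25.
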